4.7 Special Situations

1. *Pregnancy*: If a subject becomes pregnant, she will be advised to notify her obstetrician of study agent exposure. The subject will not be included in the immunogenicity evaluations from her estimated date of conception even if the pregnancy ends early. If the pregnancy occurs prior to Study Day 90, she will be encouraged to remain in the study for periodic safety evaluations and will be followed until completion of her pregnancy or the end of the study. The subject will be asked to sign a release of medical information form so that records can be obtained from her pregnancy provider regarding the outcome of the pregnancy. If a subject becomes pregnant after Study Day 90, but before Study Day 360, she will be withdrawn from the study. (See Investigator Reporting Responsibilities – Section 8.5).
2. *Lost to follow-up*: A subject who cannot be contacted by telephone or other means of communication, including U.S. mail, is considered lost to follow-up. A subject may be

considered lost to follow-up and withdrawn from the study once 3 attempts to contact the subject by any means and a certified letter sent to the last known address have failed to elicit a response from the subject.

3. *Incarceration:* If a subject becomes incarcerated during the course of the study, he or she may be terminated from the study if the period of incarceration renders him or her unable to complete the study. Alternatively, a subject who received the investigational product and was subsequently incarcerated may be taken “off treatment” rather than withdrawn to facilitate continued safety monitoring upon release.

5. VACCINE PREPARATION

5.1 Supplies

Monovalent Influenza Subvirion Vaccine (H5N1) vaccine, lot number UD08916, will be supplied in multiuse vials by BARDA. Vaccine for this protocol will be stored at the Division of Microbiology and Infectious Diseases (DMID), National Institutes of Health (NIH), repository until requested by the Center for Immunization Research (CIR). Vaccine will be formally requested to be transferred to the Pharmacy and Investigational Drug Service (IDS), Room 100 Osler at the Johns Hopkins Hospital by the Principal Investigator (PI) after IRB and FDA approval for the study has been granted. Vaccine will then be stored at the IDS. On the day of vaccination, the PI or designated clinical investigator will supply to the pharmacy individual participant specific vaccine request form (prescription) for each subject to be vaccinated. Each individual subject prescription will include the protocol number, the vaccine name, the vaccine dose, the investigational new drug (IND) number, and the number and name of the subject to be vaccinated. The IDS requires that the name be included and keeps these requests in a locked file as part of the study documents. The Pharmacist will draw up the vaccine from the multi-dose vials into syringes, 0.5 mL vaccine/syringe (45 µg dose, 10 per vial) based on the number of subjects to be vaccinated. The pharmacist will label each syringe with the study product name, PI initials, study number, subject number, preparer and study product verifier’s initials and expiration date and time. He or she will supply the appropriate number of syringes to the investigator. The vaccine will be transported to the investigator on wet ice or using cool packs for administration at the vaccination site on the same day.

5.2 Vaccine Storage and Accountability

Vaccine will be stored at 2° to 8°C. **Vaccine should not be frozen.** Vaccine will be shipped to the IDS from the DMID repository with cool packs and a temperature log to ensure that the vaccine remained within the acceptable range. Vaccine cannot be used until it is verified by the Sponsor that the temperature has stayed within range. If during shipping, the vaccine falls out of the acceptable range, it will be quarantined until BARDA has been contacted and has determined whether or not it is acceptable to use the shipment. If not, it will be disposed of per BARDA’s instruction, and a new shipment will be requested. Once at the IDS, vaccine will be stored in temperature-monitored refrigerator, and the logs will be available for the monitors, if they wish to see them. In transport from the IDS, a study specific procedure re: “The transport of Investigational Agent for administration to study subjects” will be followed.

5.3 Disposition of Used/Unused Supplies

At the time of study product administration, the study product administrator and verifier will initial the label and remove one of two detachable labels from the syringe and place it on a piece of paper (labeled with the CIR study number, the subject's study ID number, and the time of virus administration). The paper with the labels will be kept in the Study Binder. The other label will be placed in the subject chart as source documentation. The study product administration time will be documented on the Study Product Administration Record (SPAR). A copy of the completed SPAR will be placed in the Study Binder. The original will be returned to the CIR laboratory personnel along with any unused supply. The SPAR will be maintained in the laboratory and filed in the accountability binder. Used syringes will be disposed of in a sharps container. Any unused syringes will be returned to the pharmacy with the labels intact and will be documented on the accountability log by the pharmacist as unused. The Pharmacist will also document the use of multi-dose vials. All open multi-dose vials and unused syringes will be destroyed by the pharmacy according to pharmacy specific procedures. Unopened vials will be kept by the pharmacy until instructed by the Sponsor. In this manner, monitoring personnel will be able to account for all vials and syringes used for the study.

6. STUDY PROCEDURES

6.1 Recruitment and Screening (Up to 60 Days Prior to Vaccination)

Subjects will be evaluated, initially, through a JHBSPH IRB-approved general screening protocol – JH200 (IRB# H22040219A2). This general screening protocol is used to identify subjects who may be eligible to participate in a vaccine trial.

6.2 Recruitment

The CIR disseminates information about opportunities to participate in its vaccine clinical trials via IRB-approved content on its own website (centerforimmunizationresearch.org), social media platforms, YouTube, and in web, newspaper, radio and television advertisements. Study specific IRB-approved fliers and brochures are distributed locally.

Cohort 1 will consist of prior recipients of Live Attenuated H2N2, H6N1 and H9N2 Influenza Vaccines as participants in previous CIR studies (CIR 211, CIR 247, CIR 251). With each initial and subsequent telephone contact, subjects are asked if they will allow us to call them about opportunities to participate in future studies. The response to this question is documented on a pre-screening assessment form and in the CIR Adult Studies Data Base. Study staff has compiled a list of approximately 63 volunteers who participated in these three studies from 2005 - 2009. They will be contacted via phone, and/or IRB-approved letter, and invited to participate in our general screening study to see if they would be eligible and willing to participate in this study as recalled subjects. After this initial contact, subjects will be referred to the telephone recruiter. The recruiter will administer a brief qualifying phone screen after obtaining verbal consent and eligible recruits will be scheduled for in-person screening visits according to their interests and availability.

Cohort 2 – the control cohort consisting of LAIV-naïve/H5 antibody negative subjects, will be identified as individuals who make inquiries by telephone call or email to the clinical trial site. A telephone recruiter will respond to calls and emails and provide brief scripted descriptions of currently accruing CIR trials as specified in the CIR’s general screening protocol. The recruiter will administer a brief qualifying phone screen after obtaining verbal consent and eligible recruits will be scheduled for in-person screening visits according to their interests and availability.

The screening evaluation outlined below will be completed within 60 days prior to vaccination. During the initial in-person screening visit trained study staff will:

1. Provide a copy of the screening study consent form and encourage the volunteer to read the consent and ask questions
2. Administer a brief, written comprehension assessment to confirm understanding of the screening study procedures and requirements
3. Obtain written, informed consent from the subject indicating willingness to participate in the CIR JH200 Screening Protocol as evidenced by subject signature, date and time on the informed consent document. The staff person obtaining consent will sign, date and time the ICF document. A copy of the signed document will be given to the subject. The original will be kept in the subject chart.
4. Elicit a complete medical history, including current medications, and, for females, menstrual and contraceptive history, assessment of childbearing potential, and/or history of surgical sterility or menopausal status
5. Provide human immunodeficiency virus (HIV) pretest counseling, including information about HIV testing, transmission, and prevention, explanation of test results, post-test counseling, results reporting, and that testing is voluntary, but necessary for study participation
6. Provide pregnancy prevention counseling for females focused on the importance of preventing pregnancy during study participation, potential risks associated with pregnancy while taking investigational drugs, effective contraceptive options, and local resources for obtaining family planning services.
7. After review of medical history, the study nurse or nurse practitioner will offer at no cost the regular dose quadrivalent seasonal flu vaccine – Fluzone.

Additionally, the following activities may occur or be deferred to a subsequent screening visit depending on study requirements:

1. Administer a complete physical examination

2. Obtain blood for complete blood count (CBC) with differential and platelet count, hepatitis B surface antigen, hepatitis C antibody, HIV antibody (will be completed within 30 days of vaccination) and H5N1 HAI assay. Urine will be collected from females for β -HCG testing.

6.3 CIR 327 Study-Specific Screening and Informed Consent

After the initial screening process has been completed, Subjects will be notified of their eligibility for further screening. All clinically significant abnormalities will be reviewed with the subjects and referrals for follow-up care will be provided. Subjects who test positive for hepatitis B, hepatitis C, or HIV) will be notified and referred to the Baltimore City Health Department according to Maryland reporting requirements. Eligible and willing subjects will be asked to return to the CIR for study-specific screening and consent.

Informed consent is an ongoing process that includes the informed consent document and continues throughout the trial. Trained study staff will initiate the consenting process as follows

1. Potential study participants will be given a copy of the IRB-approved study consent document to read.
2. Subjects will be encouraged take as much time as they need and to ask questions
3. Subjects will be asked to complete multiple-choice/fill in the blank questionnaire to evaluate comprehension of study aims, procedures, requirements, and risks.
4. Subjects will meet privately with study staff to review the completed comprehension assessments to identify gaps in subjects' understanding of study rationale, requirements, and risks, and their role as study participants.
5. Study staff will review the pertinent study information with the subject until the subject verbalizes understanding. The subject may be offered up to 2 more attempts to answer 70% or more of the questions correctly.
6. Subjects achieving a score of 70% or better and verbalizing willingness to participate in the study will be asked to indicate their consent in writing by signing the informed consent document and recording date and time that consent was given.
7. **The staff person obtaining consent will sign, date and time the ICF document. A copy of the signed document will be given to the subject. The original will be kept in the subject chart.**

After obtaining informed consent the following procedures may be completed

1. A complete physical exam if not done during the general screening visit or at the discretion of the PI or designee.
2. No cost flu vaccine will be offered to subjects who declined flu vaccination during initial screening. Subjects who continue to decline the flu vaccine will be counseled as to the benefits of annual seasonal flu vaccine and risk of illness due to declining or delaying vaccination. Subjects will be offered the option of deferring study enrollment for 30 days if they choose to accept the flu vaccine.
3. Any laboratory assays or screening procedures mentioned above that were not completed during the first screening visit (or if assays need to be repeated), may be completed during the study specific screening visit. Urine will be collected from females for β -HCG testing.

6.4 Immunization Procedure

Syringes prepared by the IDS and placed in cold box (as per Section 5.1 above) will be removed in order as subjects receive vaccination. The syringe will be warmed briefly, the subject number will be verified, and then the vaccine will be administered intramuscularly (IM) in the deltoid muscle to eligible and consenting subjects. Empty syringes will be disposed of in an appropriate sharps container.

6.5 Clinical Evaluation

Vital signs (temperature, heart rate, respiratory rate, and blood pressure) will be assessed during screening, pre and 30 minutes post vaccination, Day 7 and Day 14. Focused physical examinations (examination of head, eyes, ears, nose, throat, heart and lungs) will be performed on the day of vaccination and at Day 7 and as indicated by interim history to day 360.

6.6 Treatments that Could Potentially Interfere with Vaccine-Induced Immunity

The following criteria will be reviewed with the subjects during each follow up visit up to and including day 90. If any of these become applicable during the study, it will be noted in the subject's record. The subject will not be included in further immunogenicity evaluations as of the visit in which the exclusionary treatment was reported. Subjects will be encouraged to participate in the safety evaluations, including blood draws at the discretion of the investigator for the duration of the study.

1. Use of any investigational drug or investigational vaccine other than the study article within 90 days of receipt of the study agent.
2. Administration of chronic (defined as more than 14 days) immunosuppressants or other immune-modifying drugs (topical and nasal steroids are allowed).
3. Receipt of any licensed vaccine in the 4 weeks after vaccination.
4. Receipt of immunoglobulins and/or any blood products.

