2. OBJECTIVES

2.1 Primary Objective:

To explore the difference in the stalk antibody response against Influenza A group 1 stalks as measured by enzyme-linked immunosorbent assay (ELISA) and neutralization titer after receipt of the Monovalent Influenza Subvirion Vaccine (H5N1) in previous recipients of H2N2, H6N1 and H9N2 pLAIVs compared with healthy, pLAIV-naïve individuals.

2.2 Secondary Objective:

Assess the reactogenicity of the Monovalent Influenza Subvirion Vaccine (H5N1) in previous recipients of live attenuated influenza vaccine (LAIV) compared with healthy, pLAIV-naïve individuals.

Adverse events will be assessed, graded and recorded for 28 days after vaccination. Serious Adverse Events (SAEs) will be assessed for 90 days after the immunization.

2.3 Exploratory Objectives:

- To assess the biological activity of antibodies to the HA stalk region by passive transfer of serum from study subjects to mice to assess their ability to protect the mice from lethal challenge with an influenza virus.
- To correlate ELISA and neutralizing stalk antibody titers with functional ability of the post vaccine serum to protect mice from lethal challenge.
- To assess the breadth of the vaccine induced antibody response.
- To assess plasmablast and memory B cell responses to the pISV in the previous pLAIV recipients compared with naïve individuals.
- To assess the longevity of the stalk antibody response.
- To determine the titer of anti-H5 head antibodies in the 2 cohorts of subjects.
- To determine the titer of antibodies directed to the HA head received in the pLAIV doses.

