4.1 Inclusion Criteria

All the following criteria must be met for a subject to be enrolled in this trial:

1. Adult males and non-pregnant females between 18 years and 60 years of age inclusive.
2. General good health, without significant medical illness, physical examination findings, or significant laboratory abnormalities as determined by the investigator.
3. Available for the duration of the trial.

4. Able to demonstrate understanding of key study concepts, study rationale, and study participation requirements by scoring $\geq 70\%$ on a written comprehension assessment in ≤ 3 attempts.
5. Willingness to participate in the study as evidenced by signing the informed consent document.
6. Willingness to allow storage and testing of laboratory samples for future research.
7. Received 2 doses of live attenuated H2N2, H6N1, or H9N2 vaccine in a prior trial (Cohort 1) or H2N2, H6N1 and H9N2 naïve (Cohort 2)
8. Willingness to forego seasonal influenza virus vaccination from 1 month before vaccination until 3 months after vaccination.
9. Female subjects of childbearing potential must agree to have used effective birth control methods beginning at least one month prior to vaccination, and continuing with ‘per label/fully effective use’ for the chosen method for duration of the study, from amongst these:
 - pharmacologic/hormonal contraceptives, including oral, parenteral, subcutaneous, and transcutaneous delivery;
 - condoms with spermicide;
 - diaphragm with spermicide;
 - intrauterine device;
 - absolute abstinence from heterosexual intercourse as a matter of normal preferred lifestyle;

or must be surgically sterile or must be age 50 AND have had no menses at all for at least one full year.

All females must provide urine for pregnancy testing prior to enrollment (immediately prior vaccination), as well as a statement of menstrual history and a summary of all potentially reproductive sexual activity for the month prior to vaccination, and at each study contact throughout the study, and report known or suspected pregnancy immediately.

10. Willingness to refrain from blood donation during the course of the study.

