6.7 Concomitant Medications

A concomitant medication (con-med) is a drug or biological product, other than a study drug, taken by a subject during a clinical trial. Information about routine medication use will be documented in the screening medical history. Concomitant medications and changes in pre-existing medication regimens indicating new diagnoses or worsening of a pre-existing condition will be collected from vaccination to Day 28 to identify solicited and unsolicited AE's, new or changed significant or chronic conditions and treatments potentially interfering with vaccine immunity. Between day 28 and 90 concomitant medications will only be collected if associated with an SAE or with a treatment that interferes with vaccine-induced immunity as above.

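### Licensed influenza vaccine after Day 28 and influenza infection at any time have no analysis rule and little required recording, so the Day 360 stalk-antibody longevity sample may carry unrecorded exposure

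*Combined protocol and SAP*

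**What the plan says.** Five parts of the protocol bear on this point.

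- **Eligibility (Section 4.1, item 8):** "Willingness to forego seasonal influenza virus vaccination from 1 month before vaccination until 3 months after vaccination".
- **Analysis exclusion (Section 6.6):** for licensed vaccines the criterion is "Receipt of any licensed vaccine in the 4 weeks after vaccination". For investigational products it is "Use of any investigational drug or investigational vaccine other than the study article within 90 days of receipt of the study agent". Chronic immunosuppressants and blood products are also listed; influenza infection is not. On timing: "The following criteria will be reviewed with the subjects during each follow up visit up to and including day 90". On consequence: "The subject will not be included in further immunogenicity evaluations as of the visit in which the exclusionary treatment was reported".
- **Recording (Section 6.7):** "Between day 28 and 90 concomitant medications will only be collected if associated with an SAE or with a treatment that interferes"; the sentence then points back to the Section 6.6 list. No collection is described after Day 90.
- **Visits (Section 6.8):** the check for interfering treatments appears at Days 7, 14 and 28. Days 56, 90 and 360 list a basic history focused on acute complaints, plus blood; Day 90 adds a pregnancy test. Section 6.9 limits nasal washes to respiratory symptoms in the first 28 days.
- **Use of late samples (Sections 2.3 and 10.7):** one exploratory objective is "To assess the longevity of the stalk antibody response". Section 10 has no rule for influenza vaccination or infection during follow-up.

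**The concern.** Seasonal influenza vaccine contains an H1 component, and H1 is a group 1 haemagglutinin, the group whose stalk is being measured. The eligibility rule treats seasonal vaccine as unwelcome for 3 months, while the analysis rule ignores it after 4 weeks. Section 6.7 collects only what Section 6.6 lists, so a seasonal vaccine on Day 40 would break the subject's commitment yet trigger neither an exclusion nor a required record. After about Day 90, seasonal vaccination is unrestricted and unreviewed. Section 1.1 notes that influenza is epidemic each winter, so roughly a year of follow-up will usually meet a season.

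At stake is what a Day 360 titre means. A titre that stays up may reflect a durable response to the H5N1 vaccine or a later H1 exposure, and the data needed to tell them apart are not prospectively collected.

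**Working it through.** **Step 1: set the windows side by side.** Four weeks is 28 days, and 3 months is taken as about 90 days.

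| Period | Length | Seasonal vaccine restricted (4.1) | Licensed vaccine excludes (6.6) | Licensed vaccine must be recorded (6.7) | Samples |
|---|---|---|---|---|---|
| Day 0 to 28 | 28 days | yes | yes | yes | 7, 14, 28 |
| Day 29 to 90 | 90 − 28 = 62 days | yes | no | no | 56, 90 |
| After Day 90 to 360 | 360 − 90 = 270 days | no | no | no | 360 |

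The Day 90 visit may run to Day 90 + 14 = 104, so even a compliant subject could be vaccinated shortly before a late Day 90 draw.

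**Step 2: infection.** It is not a Section 6.6 criterion in any period. Non-serious adverse events are recorded for 28 days (Section 8.2), the same period as the nasal wash. After that, non-serious influenza would surface only if a subject raised it in the basic history, and no analysis rule would follow.

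**Step 3: review promised against review listed.** Section 6.6 promises review at every follow-up visit to Day 90. The Day 56 and Day 90 lists in Section 6.8 omit it, and Appendix A has no row for it.

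**Step 4: possible size at Day 360.** The plan gives no figure. If a share p of subjects has titres raised b-fold, the geometric mean is multiplied by b^p. Both p and b are assumptions. With p = 0.5:

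- b = 1.1: 1.1^0.5 = 1.05
- b = 1.5: 1.5^0.5 = 1.22
- b = 2: 2^0.5 = 1.41

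The range starts near 1 because Section 1.4 points both ways. It describes the effect of seasonal vaccine on stalk-specific memory B cells as minimal, but also reports a significant rise in stalk titre after pandemic H1N1 vaccine. It gives no fold value for either.

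**Step 5: cohort ratio.** It is multiplied by b^(p1 − p2), where p1 and p2 are the exposed shares in the two cohorts. If p1 = p2, this is b^0 = 1, so there is no bias in expectation.

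**Step 6: cost of dropping exposed subjects.** Section 10.2 states 80% power for a 2-fold difference with 15 pLAIV recipients; Section 10.1 gives 20 controls. The SD is not stated. Solving a two-sided t-test at 0.05 gives 1.01 on the log2 scale. With that SD, 12 against 20 gives a detectable ratio of 2.10, which matches the plan's 2.1. Applied to a late comparison (which the plan does not itself power):

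- 20% of each cohort removed: 15 × 0.8 = 12 and 20 × 0.8 = 16, power about 70%
- 40% removed: 15 × 0.6 = 9 and 20 × 0.6 = 12, power about 56%

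**The case against.** The best reply is that inclusion 8 governs conduct and Section 6.6 governs analysis, so different windows need not contradict each other; that the protocol's own background expects little stalk boosting from seasonal vaccine; and that longevity is one exploratory objective in a study that calls itself exploratory. All of that is fair, and it limits the size of the problem. It does not close the recording gap: uncertainty about the boost is a reason to collect the dates.

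A reader might also infer more than the documents support.

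- **That the cohort comparison is biased.** This needs unequal exposure. Both cohorts make the same commitment and get the same free seasonal vaccine offer before enrolment (Sections 6.2 and 6.3). Uptake of 60% against 30% with a 2-fold boost would give a spurious ratio of 2^0.3 = 1.23, but nothing in the documents suggests such a split.
- **That the primary endpoint is compromised.** Section 10.4 names no sampling day, so harm is not shown. It would arise only if Day 56 or later were used.
- **That all late samples are contaminated by vaccine.** Before about Day 90, seasonal vaccination requires breaking the commitment.
- **That excluding from the visit of report routinely leaves contaminated samples in.** If the treatment is reported at the next visit, that visit's sample is already out. The problem arises only when a report is delayed past an intervening visit, such as a Day 20 vaccine first reported at Day 56, which leaves Day 28 in.
- **That exposure could never be recovered.** Sera may be stored indefinitely (Section 7), so H1 head antibody could be tested later, and a history is taken at Day 360. Both are weaker than a dated record.

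**Conclusion.** The gap is real and worth closing. As written, the rules keep exposed late samples in the analysis and do not collect what is needed to identify them. Day 360 is most exposed. Days 56 and 90 are open to infection, and to seasonal vaccine mainly through a broken commitment. Inflation of apparent durability at Day 360 could be about 1.05- to 1.41-fold, but this rests wholly on an assumed 1.1- to 2-fold boost in an assumed half of the subjects; the true size is unknown. A bias between cohorts is possible but has no support in the documents. The consequence falls mainly on the exploratory longevity objective.

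**What to change.** 1. Reconcile Section 4.1 item 8, Section 6.6, Section 6.7 and the visit lists in Section 6.8 (with Appendix A), so that the restriction, the analysis rule, the recording and the visit prompts agree.
2. At Days 56, 90 and 360, record the date of any influenza vaccine and of any diagnosed influenza. At Day 0, record the date of the last seasonal vaccine. The Day 0 date matters because seasonal vaccine is offered at screening and the Day 0 sample is the natural baseline for fold rise.
3. Apply Section 6.6 analysis exclusions from the date of receipt when that precedes the report. Section 4.7 already does this for pregnancy, using the estimated date of conception.
4. Prespecify a sensitivity analysis that reports late titres, Day 360 longevity in particular, with and without exposed subjects. Exclusion need not be mandatory, since a cohort of 12 to 15 can ill afford the loss.

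The cost is two or three extra CRF questions at visits where a history is already taken, some rewording, and a smaller sample in the sensitivity analysis.
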